#### Analyses of Additional Secondary Efficacy Endpoints:

All analyses performed for the primary efficacy endpoint for the ITT and PP populations will also be performed for all additional secondary efficacy endpoints involving the percent change from baseline in BMD parameters. The primary analyses will use the PMM analysis with washout imputation similar to the analysis model for the primary efficacy endpoint, with the appropriate baseline covariate. Sensitivity analyses, subgroup analyses, and other supportive analyses will be performed as described in Section 4.3.1; however, a two-sided alpha level of 0.05 will be used. For these analyses, 95% CIs for the estimated treatment effects will be presented along with the estimated p-values.

While no forest plot will be generated for the additional endpoints, LS mean ( $\pm$ SE) percent changes from baseline for lumbar spine, total hip, and femoral neck will be plotted by treatment group over time using the ITT population.

Percent (%) changes from baseline in BMD will be summarized using descriptive statistics by visit (Month 3, 6, and 12) for each treatment group. LS Mean ( $\pm$ SE) percent changes from baseline BMD will be plotted by treatment group over time using the ITT population.

The primary population for the analysis of the secondary efficacy endpoints involving the bone formation marker, s-PINP, and the bone resorption marker, s-CTX, will be the ITT population. These parameters will be analyzed based on the ratio of the post-baseline value relative to the baseline value at each visit (using analysis visit windows described in Table 4). The transformation of the loge ratio of post-baseline versus baseline value (derived by dividing the post-baseline value by the baseline value and then applying the natural log transformation) will be used to normalize the distributions of the s-PINP and s-CTX parameters. The analysis comparing abaloparatide-SC with placebo will use PMM analysis with wash-out imputation as described in Section 4.3.1. Because their distribution violates normality assumptions, the bone marker data will be transformed using natural log transformation before imputation; and the observed and imputed data will be back-transformed after imputation. The relative treatment effect, defined as the exponential of the least squares mean difference in loge ratio between the two treatment groups at each visit will be presented along with the estimated p-values and 95% confidence intervals. Sensitivity analyses using a MMRM model, as with the primary efficacy endpoint, will also be conducted. Any value of s-PINP or s-CTX that is provided as "< numeric value" or "> numeric value" will be imputed as the numeric value in all summary tables and analyses; but will be shown with the actual result in the listings.

Geometric mean values, geometric mean values ( $\pm$ SE) relative to baseline, mean ( $\pm$ SD) change from baseline values, and mean ( $\pm$ SD) percent change from baseline values at each visit for s-PINP and s-CTX will be tabulated using descriptive statistics. Geometric mean ( $\pm$ SE) of the ratio relative to baseline as well as mean ( $\pm$ SE) percent changes from baseline for s-PINP and s-CTX will be plotted by treatment group over time using the ITT population. Plots will also be

presented for the median ( $\pm$  interquartile range) for the raw values of s-PINP and s-CTX over time by treatment group.

A BMD responder analysis will be performed for exploratory purposes. This analysis will be based on the ITT population. Three categories of BMD response will be evaluated: % BMD increase >0%, >3%, and >6%. The by-visit responses (using analysis visit windows described in Table 4) will be assessed at the lumbar spine, total hip, and femoral neck. For the "all sites" analysis, subjects who have the pre-specified percentage BMD increase at all three anatomical sites at the same visit will be considered responders. A subject must have non-missing BMD results at all three sites at the same visit to be included in the "all sites" analysis. No imputation of missing data will be implemented. For the "all sites" analysis, the BMD response status at end of study will also be summarized. In this analysis, the "all sites" response status will be based on the subject's last BMD assessment during the study. If the last BMD assessment is missing the result for one or two anatomical site(s), the subject will be classified as a non-responder at End of Study. The denominator for the percentage of BMD responders at End of Study will be the number of subjects in the ITT population who had both a baseline and a post-baseline BMD.

BMD responder analyses will also be performed at each of the three anatomical sites separately, using the same three categories of BMD response used in the "all sites" analysis. A subject must have non-missing BMD results at a given visit to be included in the by-visit analysis. No imputation of missing BMD data will be implemented.

The primary time point for all BMD responder analyses is Month 12. The chi-square test will be used to explore the difference in the number (%) of responders between the two treatment groups at each visit (Months 3, 6 and 12) for each category of response. If the number of responders is less than five in any treatment group, the Fisher's exact test will be used. No multiplicity adjustment to the p-values for the BMD responder analysis will be implemented.

Analysis of the time to new clinical fracture during the study will be performed for exploratory purposes. Duration in days from the date of randomization to the first incidence of clinical fracture will be derived. The crude incidence rates of new clinical fracture, Kaplan-Meier estimates of the incidence rate at Month 12, hazard ratio (95% CI) based on a Cox proportional hazard model, Kaplan-Meier curves, and p-values from the log-rank test for the comparison of the treatment groups will be generated using the ITT and PP populations for this time-to-event variable. If a subject does not experience any clinical fracture over the 12 months of treatment plus the 30-day follow-up, this subject will be censored at the last known day in the study up to the follow-up visit.

The number and percentage of subjects for whom disease status has changed from osteoporosis at baseline to osteopenia or to normal (Refer to Section 4.3.2 for the definitions of osteoporosis, osteopenia, and normal), or no change at end of treatment will be tabulated; and will be analyzed using the Cochran-Mantel-Haenszel (CMH) test stratified by baseline disease status for the ITT population. No imputation of missing BMD data will be implemented.

The percent change from baseline in total hip and femoral neck volumetric BMD (vBMD) at Month 12, as measured by quantitative computed tomography (QCT), will be analyzed using an ANCOVA model with fixed effects of treatment and DXA instrument manufacturer, and with the relevant vBMD baseline value as covariate for the ITT population. No imputation of missing vBMD data will be implemented.

Study BA058-05-019 SAP

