The analyses of the key secondary BMD endpoints will be performed using a PMM analysis with multiple imputation using the wash-out imputation method similar to the analysis for the primary efficacy endpoint, as stated in Section 8.4.2, with the appropriate baseline covariate. Sensitivity analyses using MMRM models, sensitivity analyses for addressing the effect of the COVID-19 pandemic, and supportive analyses using the LOCF method, as with the primary efficacy endpoint, will also be conducted.

The bone formation marker, s-PINP, and the bone resorption marker, s-CTX, will be analyzed based on the ratio of the post-baseline value relative to the baseline using a natural log transformation at each visit. The analysis will use a PMM analysis with multiple imputation using the wash-out imputation method similar to that described in Section 8.4.2.
Percent changes from baseline in BMD over time will be summarized using descriptive statistics by visit for each treatment group.

The bone formation marker, s-PINP, and the bone resorption marker, s-CTX, will be summarized descriptively by treatment group, with values, changes and percent changes from baseline, geometric mean values, and geometric mean values relative to baseline at each visit.

A BMD responder analysis by visit will be performed for those subjects who have both baseline and the relevant post-baseline BMD values. Three categories of BMD response will be evaluated: %BMD increase > 0%, > 3%, and > 6%. The response will be assessed at the lumbar spine, total hip, and femoral neck. Subjects who have BMD increase at all 3 skeletal sites at the same visit will be considered responders, with the primary time point at 12 months. No imputation of missing data will be implemented. The number and percentage of responders in each treatment group will be compared using either the Chi-square test or Fisher's exact test.

Kaplan-Meier estimates for the time to new clinical fracture at 12 months and the hazard ratio (99% CI) will be presented, with treatment comparisons based on the log-rank test.

The number and percentage of subjects for whom disease status (categories as defined in the secondary endpoints listed earlier in this section) has changed from osteoporosis at baseline to osteopenia, normal, or no change at 12 months will be analyzed using the Chi-square test.

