- 1. Intermittent missing data in the placebo treatment group will be imputed using MCMC methods, assuming MAR. SAS PROC MI will be utilized for this step using the MCMC impute=monotone option. A total of 100 datasets will be created. These datasets will be utilized in Step #2.
- 2. The remaining missing values in the placebo group with a monotone missing data pattern will be imputed in this step. Missing data will be imputed assuming data are MAR. Only data (both observed and imputed) from subjects in the placebo group will be utilized in this step. SAS PROC MI will be used to impute missing values utilizing the monotone reg option. This will be performed for the 100 datasets. After this step, the 100 datasets will be fully imputed for the placebo treatment group.
- 3. The missing values at Month 12 in the abaloparatide-SC group will be imputed in this step. Control-based PMM imputation will be performed. With this imputation model, the missing values in the abaloparatide-SC group will not be constructed from the observed data in the abaloparatide-SC group but rather from the observed baseline and data (including imputed values) from the placebo group at Month 12. The MNAR statement in SAS PROC MI will be used to impute missing values. This will be performed for the 100 datasets.
- 4. A total of 100 fully imputed datasets will be created for both treatment groups. Since multiple imputation is a stochastic method, slight differences in output can be expected for different initial states of the random number generator. The seed numbers will be identified in the SAS programs to allow for reproducibility.

- 5. After the missing data imputation is completed using the above steps, percentage change values will be calculated in each of the imputed datasets at each visit.
- 6. These 100 datasets will be analyzed using ANCOVA models with fixed effect of treatment group and DXA instrument manufacturer, and baseline lumbar spine BMD as a covariate for the primary efficacy endpoint.
- 7. Treatment effects (difference in LS means between treatments) from these 100 analyses will then be combined using Rubin's Method via SAS PROC MIANALYZE procedure for the primary endpoint.

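### The s-PINP and s-CTX models do not name the marker's own baseline as a covariate; adding it is a free improvement, though the documents do not fix the size of the gain

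*SAP*

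**What the plan says.** SAP 4.3.2 (Analyses of Additional Secondary Efficacy Endpoints) analyses s-PINP and s-CTX as the natural log of follow-up over baseline. For the model it says: "The analysis comparing abaloparatide-SC with placebo will use PMM analysis with wash-out imputation as described in Section 4.3.1". The marker MMRM is likewise defined only by pointing to the primary endpoint. The marker paragraph names no covariate.

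SAP 4.3.1, step 6, fits the ANCOVA "with fixed effect of treatment group and DXA instrument manufacturer, and baseline lumbar spine BMD as a covariate for the primary efficacy endpoint". The MMRM in 4.3.1 uses the same two adjustment terms, plus visit and treatment-by-visit.

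Elsewhere the SAP adapts the covariate to the endpoint. The key secondary and additional BMD endpoints use a model "similar to the analysis model for the primary efficacy endpoint, with the appropriate baseline covariate". The QCT endpoints have the "relevant vBMD baseline value as covariate for the ITT population".

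The protocol does not fill the gap. Section 8.4.3 gives the markers a "wash-out imputation method similar to that described in Section 8.4.2", and the synopsis refers back to the BMD method. Neither names a marker covariate.

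**The concern.** SAP 3.6 promises that covariate adjustments will be set out in Section 4. For the markers, Section 4 supplies either the lumbar spine terms by reference or nothing. Because the SAP reports a least squares mean difference, a fitted model is intended and its terms need to be known.

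A programmer who follows the text literally would adjust a serum marker for a bone density value and a densitometer brand, and would leave out the one baseline variable with an obvious link to the outcome. That value is already measured on Day 1. At stake are precision and prespecification for eight additional secondary comparisons: s-PINP and s-CTX at Months 1, 3, 6 and 12.

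**Working it through.** **No plan figure to reproduce.** The sample size statements (SAP 3.1, Protocol 8.5) cover BMD only. The documents give no SD, correlation or power for either marker, so r and k below are assumptions.

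**Set-up.** Let s² be the variance of log baseline, k the ratio of the SD of log follow-up to the SD of log baseline, and r their correlation. Take r and k as the same in both arms.

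- Variance of the log ratio, baseline not a covariate: s²(1 + k² − 2rk).
- Residual variance with log baseline as covariate: s²k²(1 − r²).
- Difference: s²(1 − 2rk + r²k²) = s²(1 − rk)².

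The difference is a square, so it is never negative. It is zero only when rk = 1, which is the one case where the fixed slope of 1 built into the log ratio is the best slope. This gives the direction without any assumed value.

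**Size.** The ratio of interval widths, without over with the covariate, is √[(1 + k² − 2rk) / (k²(1 − r²))]. Examples:

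- k = 1, r = 0.3: √(1.4 / 0.91) = 1.240
- k = 1, r = 0.5: √(1.0 / 0.75) = 1.155
- k = 1, r = 0.9: √(0.2 / 0.19) = 1.026
- k = 1.25, r = 0.8: √(0.5625 / 0.5625) = 1.000
- k = 0.8, r = 0.3: √(1.16 / 0.5824) = 1.411

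| k | r = 0.3 | r = 0.5 | r = 0.7 | r = 0.8 | r = 0.9 |
|---|---|---|---|---|---|
| 0.8 | 1.411 | 1.323 | 1.262 | 1.250 | 1.282 |
| 1.0 | 1.240 | 1.155 | 1.085 | 1.054 | 1.026 |
| 1.25 | 1.129 | 1.058 | 1.010 | 1.000 | 1.026 |
| 1.5 | 1.071 | 1.018 | 1.001 | 1.024 | 1.134 |

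**Check at the planned size.** I simulated complete data at 150 versus 75 with a two-level manufacturer factor in both models. The literal model used baseline BMD and the alternative used baseline marker. With k = 1 and BMD unrelated to the marker, the ratios were 1.245, 1.155, 1.086 and 1.026 for r = 0.3, 0.5, 0.7 and 0.9. With a BMD–marker correlation of −0.2 they were 1.233, 1.149, 1.082 and 1.025. So baseline BMD recovers almost none of the loss.

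**Chance imbalance.** The slope of the log ratio on log baseline is rk − 1. A chance difference d between arms in mean log baseline therefore moves the unadjusted estimate by (rk − 1)d. The same Day 1 value is the denominator at all four visits, so for a given marker the four estimates share that baseline difference.

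**The case against.** The strongest reply is that the SAP does not prescribe the wrong model. Step 6 limits lumbar spine BMD to being the covariate "baseline lumbar spine BMD as a covariate for the primary efficacy endpoint", the protocol says the marker method is similar rather than identical, and everywhere else the SAP adapts the model it uses the endpoint's own baseline. On that view the cross-reference carries only the missing-data method. This stands in part: a reader might infer that the sponsor has decided to adjust the markers for lumbar spine BMD, and no sentence says so. What remains is that the literal reading omits the baseline marker and no sentence puts it in.

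A reader might also infer that baseline is ignored and imbalance left uncorrected. That is not supported. Baseline is subtracted on the log scale with slope 1, and step 3 of SAP 4.3.1 builds the imputed values "rather from the observed baseline and data (including imputed values) from the placebo group at Month 12", which for a marker would naturally be its own baseline. Only an estimated slope in the analysis model is missing.

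Nor do the documents show that the log ratio depends strongly on baseline, so no single percentage can be claimed. A gain of 8% to 19% in interval width, for instance, needs both r between 0.7 and 0.3 and equal SDs (1/1.085 = 0.92; 1/1.240 = 0.81).

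Finally, the vBMD endpoints "will be analyzed using an ANCOVA model with fixed effects of treatment and DXA instrument manufacturer", and a reader might want that factor removed too. That model already has its own baseline, and no gain from removing the factor has been shown, so no change is proposed there.

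**Conclusion.** This is a free improvement, not an error that threatens a conclusion. As written, the marker ANCOVA and MMRM do not include the baseline marker as a covariate. Adding it cannot cost precision in large samples and gains some unless rk = 1. Without it, intervals are about 3% to 24% wider when the SDs are equal (r from 0.9 to 0.3). Over k from 0.8 to 1.5 the penalty runs from none to about 40%.

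These figures rest on assumed r and k, on both being common to the two arms, and on complete data; imputation variance is not modelled. Randomisation keeps the treatment estimate essentially unbiased either way. The marker endpoints lie outside the fixed sequence (SAP 3.7) and are assessed nominally at 0.05 (SAP 4.3), so the lumbar spine, total hip and femoral neck tests do not change.

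**What to change.** In the marker paragraph of SAP 4.3.2, specify the ANCOVA as log ratio on treatment and log baseline of the same marker, in place of baseline lumbar spine BMD and DXA manufacturer. Specify the MMRM with the same two terms plus visit and treatment-by-visit. Leave the vBMD model as it is.

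The cost is a sentence or two, agreed before database lock and unblinding. No new data are needed. The baseline value is already required to form the ratio, so no subject is lost from the analysis by adding it.

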2.2. Secondary Endpoints

The key secondary efficacy endpoints are:

- Percent change from baseline in total hip BMD at 12 months
- Percent change from baseline in femoral neck BMD at 12 months

Additional secondary efficacy endpoints are:

- Percent change in baseline in:
 - Lumbar spine BMD at 3 and 6 months
 - Total hip BMD at 3 and 6 months
 - Femoral neck BMD at 3 and 6 months
 - Ultra-distal radius BMD at 3, 6, and 12 months
 - Distal one-third radius BMD at 3, 6, and 12 months
- Log ratio of post-baseline over baseline in:
 - Serum procollagen type I N-terminal propeptide (s-PINP) at 1, 3, 6, and 12 months
 - Serum carboxy-terminal cross-linking telopeptide of type I collagen (s-CTX) at 1, 3, 6, and 12 months
- Proportion of subjects experiencing BMD gains from baseline of > 0%, > 3%, and > 6% at the lumbar spine, femoral neck, and total hip at 3, 6, and 12 months
- Incidence of new clinical fractures at 12 months
- Proportion of subjects converting from the categories of osteoporosis to osteopenia or to normal at 12 months, where:
 - Osteoporosis is defined as lumbar spine or total hip BMD T-score \leq -2.5.
 - Osteopenia is defined as as one of the following:
 - \circ Lumbar spine > -2.5 and total hip BMD T-score > -2.5 and < -1.0
 - \circ Lumbar spine > -2.5 and < -1.0 and total hip BMD T-score > -2.5
 - Normal is defined as lumbar spine and total hip BMD T-score \geq -1.0.

• The percent change in total hip and femoral neck volumetric BMD as measured by quantitative CT (QCT) from baseline to 12 months QCT will be performed in a subset of subjects in a selected number of study sites.

For those subjects who consent to PK sample collection, the PK endpoints are:

- The plasma concentration of abaloparatide based on sparse PK sampling at the following visits:
 - Month 6: postdose PK samples collected 45 minutes (±15 minutes) and 2.5 hours (±0.5 hour) after abaloparatide-SC injection
 - Month 9: postdose PK samples collected 20 minutes (±10 minutes) and 4 hours (±0.5 hour) after abaloparatide-SC injection
 - Month 12: a predose sample and a postdose sample collected 1.5 hours (±0.5 hour) after abaloparatide-SC injection

The safety endpoints are:

• Overall safety and tolerability of abaloparatide-SC in men with osteoporosis as assessed by AEs, vital signs, electrocardiograms (ECGs), laboratory tests of chemistry and hematology, urinalysis, local tolerance, and presence of antibodies

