#### **3** GENERAL STATISTICAL METHODS

### 3.1 Sample Size Planned and Specified in the Protocol

A study sample size of 225 subjects (150 in the abaloparatide-SC group and 75 in the placebo group) will provide at least 99% power to detect a mean difference of 6.5% in the percentage change from baseline in lumbar spine BMD at 12 months between the abaloparatide-SC and the placebo groups at a two-sided alpha level of 0.01, assuming a standard deviation (SD) of 6.0% and a drop-out rate of 10%. For the key secondary endpoints, a total sample size of 225 subjects will have 96% power to detect a 2.2% mean difference (SD=3.5%) of percent change in total hip BMD at 12 months, and 80% power to detect a 2.0% mean difference (SD=4.1%) of percent change in femoral neck BMD at 12 months.

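### The by-visit BMD responder analyses are labelled ITT but count only men with a scan in the visit window, while mean BMD change at the same site and visit uses wash-out imputation over all randomized men

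*SAP*

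**What the plan says.** Protocol section 2.2 lists, as an additional secondary endpoint, "Proportion of subjects experiencing BMD gains from baseline of" more than 0%, 3% and 6% at the lumbar spine, femoral neck and total hip at 3, 6 and 12 months. Protocol section 8.4.3 restricts the analysis: "A BMD responder analysis by visit will be performed for those subjects who have both baseline and the relevant post-baseline BMD values". It rules out imputation, yet also says the primary analyses of the secondary efficacy variables are on the ITT population.

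SAP section 4.3.2 calls the responder analysis exploratory, bases it on ITT and names Month 12 as its primary time point. For each single site, "A subject must have non-missing BMD results at a given visit to be included in the by-visit analysis". The by-visit all-sites version needs results at all three sites. A separate all-sites End of Study table uses the last BMD assessment, counts a partly missing last assessment as non-response, and keeps every ITT man with a baseline and a post-baseline BMD.

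For change in disease category, SAP section 4.3.2 again names ITT and states: "No imputation of missing BMD data will be implemented". The time point is the end of treatment, which SAP section 5 substituted for 12 months.

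For percent change in BMD, SAP section 4.3.1 creates 100 datasets by wash-out imputation to allow for data missing not at random. SAP section 4.3.2 applies a similar analysis to the key secondary and additional BMD percent-change endpoints.

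**The concern.** A single-site responder is a man whose percent change in BMD exceeds a cut-off, so it is the same variable as the continuous endpoint, dichotomized. At Month 12 the mean change covers all randomized men and lets an abaloparatide man without data revert to placebo-like values. The responder proportion omits that man. A report could show the two side by side, both marked ITT, with different denominators and different assumptions about the same men.

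Some of the missingness depends on the outcome by design. Protocol sections 4.3.1 and 6.7 require withdrawal after a confirmed BMD loss of 7% or more at the spine or hip. Such a man is a non-responder at the affected site, but if his last scan falls before day 271 he is absent from the Month 12 denominator (SAP Table 4). At stake is the reading of a secondary endpoint that will carry p-values, not the primary claim.

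**Working it through.** **Inputs from SAP section 3.1.** 150 abaloparatide and 75 placebo; two-sided alpha 0.01; drop-out 10%, not split by arm. Differences and SDs: spine 6.5 and 6.0; total hip 2.2 and 3.5; femoral neck 2.0 and 4.1 (all in %).

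**Assumptions, because the documents give no figure.** Placebo mean change 0, 1 or 2%; normal distribution; 10% of each arm without Month 12 BMD, which equates planned drop-out with a missing scan (15 of 150 and 7.5 of 75 men).

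**Reproducing the plan's figures.** Normal-approximation power is Φ(d / [SD × √(1/n₁ + 1/n₂)] − 2.576).
- Spine, 135 and 67.5 men: above 99.9% (plan: at least 99%).
- Total hip: 96.9% at 150 and 75; 95.0% after 10% drop-out (plan: 96%).
- Femoral neck: 80.9% at 150 and 75; 75.7% after 10% drop-out (plan: 80%, so that figure reproduces only on the full 225).

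The documents state no responder rate, so what follows is illustrative.

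**Responder model.** P(change > c) = 1 − Φ((c − mean)/SD), giving A for abaloparatide and P for placebo.
- Observed cases: difference = A − P.
- Wash-out, fraction m of the abaloparatide arm missing: abaloparatide rate = (1 − m)A + mP; placebo rate unchanged; difference = (1 − m)(A − P).
- Missing counted as non-response: difference = (1 − m_A)A − (1 − m_P)P.

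**Worked case: spine, >3%, placebo mean 0.** A = 1 − Φ((3 − 6.5)/6.0) = 72.0%; P = 1 − Φ(3/6.0) = 30.9%; observed-case difference 41.2 points (from unrounded rates). Wash-out: 0.9 × 72.0 + 0.1 × 30.9 = 67.9%; difference 0.9 × 41.2 = 37.0 points. Excess: 4.1 points.

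**Spine, 10% missing (points):**

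| Placebo mean | Cut-off | Observed-case difference | Wash-out difference | Excess |
|---|---|---|---|---|
| 0% | >0% | 36.1 | 32.5 | 3.6 |
| 0% | >3% | 41.2 | 37.0 | 4.1 |
| 0% | >6% | 37.5 | 33.7 | 3.7 |
| 1% | >0% | 32.8 | 29.5 | 3.3 |
| 1% | >3% | 40.4 | 36.4 | 4.0 |
| 1% | >6% | 39.6 | 35.7 | 4.0 |
| 2% | >0% | 29.1 | 26.2 | 2.9 |
| 2% | >3% | 38.7 | 34.8 | 3.9 |
| 2% | >6% | 40.9 | 36.8 | 4.1 |

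With placebo mean 0, the excess is 1.0 to 2.4 points at the total hip and 0.9 to 1.9 at the femoral neck. In relative terms the observed-case difference is 1/(1 − m) times the wash-out one: 5% larger at 5% missing, 11% at 10%, 25% at 20%.

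**Does the direction hold under other mechanisms?** Spine, placebo mean 0:
- Missing completely at random: no bias.
- Non-response counting, 10% missing in each arm: the same differences as wash-out.
- Non-response counting, 15% abaloparatide and 5% placebo: >0%, 0.85 × 86.1 − 0.95 × 50.0 = 25.7 points (observed 36.1); >3%, 31.9 (observed 41.2).
- Non-response counting, 5% abaloparatide and 15% placebo: >0%, 0.95 × 86.1 − 0.85 × 50.0 = 39.3 points (observed 36.1); >3%, 42.2 (observed 41.2). Here observed cases understate the difference.

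**The case against.** The strongest reply is that the rule is deliberate, open and of low consequence. The protocol already specified observed cases without imputation. The SAP calls the analysis exploratory with unadjusted p-values, and it lies outside the fixed sequence. The all-sites End of Study table keeps men who miss Month 12 if they have any post-baseline scan. All of this stands and limits the weight of the point. It does not remove the conflict between label and rule, or the absence of a missing-data check on the single-site results. The protocol also still lists these proportions as secondary endpoints.

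Three stronger readings are tempting and are not supported.
- A reader might infer that the analysis is biased in favour of the drug. The documents give neither drop-out by arm nor the mechanism, and the last calculation above reverses the sign.
- A reader might infer that only completers count, or that every man who stops treatment leaves the denominator. The criterion is a scan in the window. Withdrawn men are encouraged to have the Month 12/Early Termination procedures, which include DXA, and SAP Table 4 assigns any scan from day 271 to Month 12.
- A reader might infer that disease conversion drops early stoppers in the same way. The SAP does not say which scan is the end-of-treatment scan. If it is the early-termination scan, those men are included.

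**Conclusion.** The point holds as an inconsistency. By-visit responder results are observed-case under an ITT label, while the continuous endpoint built from the same BMD values uses wash-out imputation.

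Measured against the plan's own wash-out assumption, the excess in the abaloparatide responder rate and in the treatment difference is about 3 to 4 points at the spine, on observed-case differences of 29 to 41 points. At the hip sites it is about 1 to 2.5 points. The placebo rate does not move. These sizes rest on the normal model, 10% of the abaloparatide arm missing Month 12, and an assumed placebo mean (0 to 2% at the spine, 0 at the hip sites). Overstatement is a statement relative to wash-out, not an established fact.

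For disease conversion, the supportable point is narrower: the scan is undefined and no missing-data sensitivity analysis is planned. The primary and key secondary conclusions at the 1% level do not change.

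**What to change.** 1. **Single sites, Month 12.** In each of the 100 wash-out-imputed datasets created for that site's percent-change analysis, derive status at >0%, >3% and >6%. Combine the responder rates and their difference by Rubin's rules. Step 5 of SAP section 4.3.1 already computes percent change in each dataset. The steps are written out for the spine; the SAP should confirm that the total hip and femoral neck follow them.
2. **Present tables.** Keep them as supportive and label them observed cases, with the number of men contributing per arm. Months 3 and 6 can stay in this form: Month 12 is the primary responder time point, and the written abaloparatide imputation step names Month 12 only.
3. **All sites and disease conversion.** The imputed datasets cannot simply be reused here, because these outcomes need joint imputation across sites, which is not planned. Add a sensitivity analysis over all randomized men with missing counted as non-response. Report it with drop-out by arm, since the sign of the change depends on it.
4. **Conversion scan.** State which scan is the end-of-treatment scan, and whether an early-termination scan qualifies.

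The cost is SAP wording and modest programming, with no new data. The responder difference may come out slightly smaller.
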